9.4.3 ANALYSIS OF THE SECONDARY ENDPOINT(S)

Analysis of secondary endpoints (see **Section 9.1, Statistical Hypotheses**) is not dependent on findings for the primary endpoint. Analysis of secondary endpoints is as described above for the primary endpoint (**Section 9.4.2, Analysis of the Primary Endpoint(s)**).

For Secondary Endpoint 1 (perceptual accuracy of full 30-item target set), perceptual accuracy analysis procedures are as described above for the primary endpoint. For Secondary Endpoint 2 (ICS) and Secondary Endpoint 3 (FOCUS), we use mean score across items. For Secondary Endpoint 4 (TOCS+), we use the mean percentage accuracy across listeners. Variables entered into analyses are change scores computed based on the same timepoints as for the primary endpoint as described above (**Section 9.4.2, Analysis of the Primary Endpoint(s)**). No imputation will be used for any missing data.

9.4.4 SAFETY ANALYSES

N/A

9.4.5 BASELINE DESCRIPTIVE STATISTICS

We will compare the pre-treatment performance between groups in each study to assess the success of randomization in producing two comparable groups. Although we do not expect any imbalance between groups, we will adjust for any differences in subsequent analyses to be sure any treatment effect is not due to potential confounds.

9.4.6 PLANNED INTERIM ANALYSES

N/A

9.4.7 SUB-GROUP ANALYSES

Sex as a biological variable will be included in all analyses, though we do not expect any sex differences.

9.4.8 TABULATION OF INDIVIDUAL PARTICIPANT DATA

Individual participant data will be listed by measure and time point.

9.4.9 EXPLORATORY ANALYSES

N/A

10 SUPPORTING DOCUMENTATION AND OPERATIONAL CONSIDERATIONS

10.1 REGULATORY, ETHICAL, AND STUDY OVERSIGHT CONSIDERATIONS

10.1.1 INFORMED CONSENT PROCESS

10.1.1.1 CONSENT/ASSENT AND OTHER INFORMATIONAL DOCUMENTS PROVIDED TO PARTICIPANTS

Consent forms (Parent Permission Form, PHI Authorization Form) describing in detail the study intervention, study procedures, and risks are given to the parent and informed consent will be documented in writing prior to starting study screening and intervention. A Study Information Sheet is used to guide age-appropriate explanation of the purpose of the study and obtain verbal assent. The following consent materials are submitted with this protocol

- Parent Permission Form
- Personal Health Information (PHI) Authorization Form
- Child Study Information Sheet

10.1.1.2 CONSENT PROCEDURES AND DOCUMENTATION

After initial contact and before their first appointment, parents receive (via e-mail or regular mail) a copy of the Parent Permission Form, a Study Information Sheet for children, and a Personal Health Information Authorization Form, to allow them to read these forms over at their leisure, discuss this opportunity at home, and generate any questions prior to the first visit.

At the first appointment, parents are provided with the Parent Permission Form. Research personnel verbally explain the form to parents and answer any questions they have. Parents who agree to the conditions described in the Parent Permission Form are asked to sign the forms. Permission is obtained from only one parent because the risks associated with this research are considered minimal. Permission may be obtained from a legal guardian if appropriate; we will require written documentation affirming the legal ability to consent to the child's general medical care; this documentation will be kept with consent documents.

The study is then explained verbally to the child in age-appropriate language using the Study Information Sheet, and questions are encouraged to ensure understanding. Children capable of giving assent will be also be asked to sign the Study Information Sheet. Per local IRB policy, clear positive affirmation by the child of assent to participate is documented by a check mark on the Parent Permission Form confirming the child's assent. Next, because we collect personal health information, parents are given a Personal Health Information Authorization Form. The purpose of this form is explained, and any questions are answered. If they agree, they are asked to sign the form. Parents receive copies of these forms for their records.

10.1.2 STUDY DISCONTINUATION AND CLOSURE

This study may be temporarily suspended or prematurely terminated if there is sufficient reasonable cause. Written notification, documenting the reason for study suspension or termination, will be provided by the Principal Investigator (PI) to study participants, IRB, and funding agency (NIH).

Study procedures, including intervention, may be discontinued for all participants under the following circumstances:

- Determination of unexpected, significant, or unacceptable risk to participants. In this trial, this refers to child frustration experienced during ASSIST intervention sessions. In this minimal risk study, we do not anticipate any significant adverse events. However, if 10 or more children in Cycle 1 or 2 experience recurrent significant or marked frustration (as described above in **Section 7.1, Discontinuation of Study Intervention/Experimental Manipulation**), subsequent cycles will not be initiated regardless of whether children withdraw (e.g., if 10 or more children with significant or marked frustration in Cycle 1, then Cycle 2 will not be initiated).
- Data that are not sufficiently complete and/or evaluable. Although unlikely, children may withdraw from the study, either because of recurrent frustration with study procedures or for other reasons. In the highly unlikely event that withdrawals exceed 5 children in any year, the research team will discuss what, if any, action should be taken to improve retention and whether to discontinue the study.
- Insufficient compliance of study staff to the protocol (i.e., significant protocol violations)

The study may resume once concerns about safety, protocol compliance, and data quality are addressed, and satisfy the funding agency and IRB.

10.1.3 CONFIDENTIALITY AND PRIVACY

Participant confidentiality and privacy is strictly held in trust by the participating investigators, their staff, and the sponsor and funding agency. This confidentiality is extended to the data being collected as part of this study. Data that could be used to identify a specific study participant is held in strict

confidence within the research team. No personally-identifiable information from the study is released to any unauthorized third party without prior written approval of the participant.

All research activities will be conducted in as private a setting as possible. Children are tested and receive treatment individually. However, because the study is conducted in the format of a camp, children and parents interact with other children and parents. Research personnel will use names for pragmatic reasons, but will share no other PHI with other children or parents.

Participants are assigned a unique ID code. The master list linking participant names and ID codes will be stored in an encrypted password-protected electronic file on the HIPAA-compliant server; a hard copy of the master list will be stored in a locked filing cabinet in a locked room. Only the Investigator and appropriate research personnel will have access to the master list on an as-needed basis.

Any identifiable data will be accessible only to qualified research personnel for research purposes and will not be shared with others, unless participants or parents provide explicit written permission to share this information (for example, to share with clinical service providers). We will provide parents with a report of the test results, which may aid in educational or clinical planning for the children. Data from this research may be used in publications and presentations, but participants will only be identified by their ID code. Audio and video recordings will only be used with authorization and for the purposes indicated on the Parent Permission Form and will never include names, addresses, or other identifying information (except for voice recording or facial images). Authorized representatives of the funding agency and the Institutional Review Board (IRB) may inspect all documents and records required to be maintained by the investigator, including but not limited to background testing and treatment progress notes for the participants in this study.

The study participant's contact information will be securely stored at each clinical site for internal use during the study. At the end of the study, all records will continue to be kept in a secure location for as long a period as dictated by the reviewing IRB, Institutional policies, or sponsor/funding agency requirements.

All paper-based PHI information is stored in locked filing cabinets in locked rooms, and all electronic PHI is stored in encrypted password-protected files on a HIPAA-compliant server accessible only via password-protected computers. Data will be retained until the participant/parent requests in writing that data be destroyed, or until seven years after the final publication resulting from this study or until seven years after the child turns 18, whichever occurs later. All information, past and current, will be used only for purposes authorized on the Parent Permission Form. The potential uses of audio and video recordings of children (in addition to research purposes) include scientific presentations and publications, non-scientific presentations and publications, and teaching purposes.

Parents and participants will be informed of all these procedures, both in person (verbally) and in writing on the Parent Permission Form. They will be informed that they may change their mind or revoke authorizations in writing at any time. Further, they will be told that they may choose to not answer any questions that they do not feel comfortable answering.

It is NIH policy that the results and accomplishments of the activities that it funds should be made available to the public (see <https://grants.nih.gov/policy/sharing.htm>). The PI will ensure all mechanisms

used to share data will include proper plans and safeguards for the protection of privacy, confidentiality, and security for data dissemination and reuse (e.g., all data will be thoroughly de-identified and will not be traceable to a specific study participant). Plans for archiving and long-term preservation of the data will be implemented, as appropriate.

10.1.4 FUTURE USE OF STORED SPECIMENS AND DATA

Data collected for this study will be stored and retained on the HIPAA-secure server hosted by Temple University. After the study is completed, the de-identified data set will be made available for use by other interested researchers, speech-language pathologists, and members of the general public upon request after submitting to the PI a data sharing agreement. Permission to make these data available is included in the informed consent. Parents are informed that they may change their mind or revoke authorizations in writing at any time.

10.1.6 SAFETY OVERSIGHT

Safety oversight will be under the direction of the PI, in consultation with Co-I [name], the SLP supervisors, and the treating SLPs. This team will meet at the end of every intervention day.

10.1.7 CLINICAL MONITORING

N/A

10.1.8 QUALITY ASSURANCE AND QUALITY CONTROL

The clinical site will perform internal quality management of study conduct, data collection, documentation and completion. Quality control (QC) procedures will be implemented as follows:

Informed consent --- Study staff will review both the documentation of the consenting process as well as a percentage of the completed consent documents. This review will evaluate compliance with GCP, accuracy, and completeness. Feedback will be provided to the study team to ensure proper consenting procedures are followed.

Source documents and the electronic data --- Data will be initially captured on source documents (see **Section 10.1.9, Data Handling and Record Keeping**) and will ultimately be entered into the study database. To ensure accuracy site staff will compare a representative sample of source data against the database, targeting key data points in that review.

Intervention Fidelity — Consistent delivery of the study interventions will be monitored throughout the intervention phase of the study. Procedures for ensuring fidelity of intervention delivery are described in **Section 6.2.1, Interventionist Training and Tracking**.

Data Collection Fidelity — The Data Collection team will receive extensive training on the data collection protocol, including a written manual, role play examples, recording equipment familiarization, and data backup. Data collection sessions are recorded (audio & video) and supervised in real time via secure video feed by the PI or Project Manager. Data Collection protocol deviations are reviewed on an ongoing basis and corrective actions will be implemented as needed.

Data Analysis — The Data Analysis team will receive extensive training on the data analysis protocol, including a written manual, playback software familiarization, and data backup. Data analysts first complete a calibration stage during which they score data from children with CAS (from prior studies in the lab). Once calibrated, all responses by all children are scored by at least two analysts and inter-rater reliability is assessed.

Protocol Deviations — The study team will review protocol deviations on an ongoing basis and will implement corrective actions when the quantity or nature of deviations are deemed to be at a level of concern.

Should independent monitoring become necessary, the PI will provide direct access to all trial related sites, source data/documents, and reports for the purpose of monitoring and auditing by the sponsor/funding agency, and inspection by local and regulatory authorities.

10.1.9 DATA HANDLING AND RECORD KEEPING

10.1.9.1 DATA COLLECTION AND MANAGEMENT RESPONSIBILITIES

Data collection is the responsibility of the clinical trial staff at the site under the supervision of the PI. The PI is responsible for ensuring the accuracy, completeness, legibility, and timeliness of the data reported. All data will be stored as described above (see **Section 10.1.3, Confidentiality and Privacy**). For the purpose of determining study eligibility based on presence of CAS, video recordings of clinical evaluation sessions (screening) are shared with external SLP experts (Drs. [name] &

[name]) via Temple University's SafeSend file sharing system (see **Section 8.1, Endpoint and Other Non-Safety Assessments**).

Source data include:

- Clinical evaluation score form and notes from screening
- Tracking sheets and clinical notes from intervention sessions
- Audio and video recordings of evaluation sessions
- Audio and video recordings of intervention sessions
- Audio and video recordings of data collection sessions
- Parent-reported questionnaires and outcome measures
- Spreadsheets with outcome data

10.1.9.2 STUDY RECORDS RETENTION

Study documents will be retained until the participant/parent requests in writing that data be destroyed, or until seven years after the final publication resulting from this study or until seven years after the child turns 18, whichever occurs later.

10.1.10 PROTOCOL DEVIATIONS

This protocol defines a protocol deviation as any noncompliance with the clinical trial protocol, International Council on Harmonisation Good Clinical Practice (ICH GCP), or Manual of Procedures (MOP) requirements. The noncompliance may be either on the part of the participant, the investigator, or the study site staff. As a result of deviations, corrective actions will be developed by the site and implemented promptly.

These practices are consistent with ICH GCP:

- Section 4.5 Compliance with Protocol, subsections 4.5.1, 4.5.2, and 4.5.3
- Section 5.1 Quality Assurance and Quality Control, subsection 5.1.1
- Section 5.20 Noncompliance, subsections 5.20.1, and 5.20.2.

It is the responsibility of the PI to use continuous vigilance to identify and report deviations within 5 working days of identification of the protocol deviation. All deviations will be addressed in study source documents, and reported to the NIDCD Program Official. Protocol deviations will be sent to the reviewing Institutional Review Board (IRB) per their policies. The PI will be responsible for knowing and adhering to the reviewing IRB requirements. Further details about the handling of protocol deviations will be included in the MOP.

10.1.11 PUBLICATION AND DATA SHARING POLICY

This study will be conducted in accordance with the following publication and data sharing policies and regulations, including the National Institutes of Health (NIH) Public Access Policy, which ensures that the public has access to the published results of NIH funded research. It requires scientists to submit final peer-reviewed journal manuscripts that arise from NIH funds to the digital archive PubMed Central upon acceptance for publication.

This study will comply with the NIH Data Sharing Policy and Policy on the Dissemination of NIH-Funded Clinical Trial Information and the Clinical Trials Registration and Results Information Submission rule. As such, this trial will be registered at ClinicalTrials.gov, and results information from this trial will be submitted to ClinicalTrials.gov. In addition, every attempt will be made to publish results in peer-reviewed journals. Data from this study may be requested from other researchers within 1 year of the completion of the primary endpoint by contacting the PI. Considerations for ensuring confidentiality of these shared data are described in **Section 10.1.3, Confidentiality and Privacy**).

10.1.12 CONFLICT OF INTEREST POLICY

The independence of this study from any actual or perceived influence is critical. Therefore, any actual conflict of interest of persons who have a role in the design, conduct, analysis, publication, or any aspect of this trial will be disclosed and managed. Furthermore, persons who have a perceived conflict of interest will be required to have such conflicts managed in a way that is appropriate to their participation in the design and conduct of this trial.

10.2 ADDITIONAL CONSIDERATIONS

N/A

10.3 ABBREVIATIONS AND SPECIAL TERMS

AE	Adverse Event
ASHA	American Speech-Language-Hearing Association
ASSIST	Apraxia of Speech Systematic Integral Stimulation Treatment
CAS	Childhood Apraxia of Speech
CAS3SLP	Childhood Apraxia of Speech 3 Speech-Language Pathologists' diagnostic rating scale
CELF	Clinical Evaluation of Language Fundamentals
CFR	Code of Federal Regulations
CMP	Clinical Monitoring Plan
Co-I	Co-Investigator
CRF	Case Report Form
CSD	Communication Sciences and Disorders

CTOPP	Comprehensive Test of Phonological Processing
CV	Consonant-Vowel
DEAP	Diagnostic Evaluation of Articulation and Phonology
DEMSS	Dynamic Evaluation of Motor Speech Skill
DHHS	Department of Health and Human Services
EVT	Expressive Vocabulary Test
FB	Feedback
FDA	Food and Drug Administration
FDAAA	Food and Drug Administration Amendments Act of 2007
FOCUS-34	Focus on Outcomes of Communication Under Six
FRS	Frustration Rating Scale
GCP	Good Clinical Practice
GFTA	Goldman-Fristoe Test of Articulation
HIPAA	Health Insurance Portability and Accountability Act
Hz	Hertz
ICC	Intra-class correlation
ICF	International Classification of Functioning and Disability
ICH	International Council on Harmonisation
ICMJE	International Committee of Medical Journal Editors
ICS	Intelligibility-in-Context Scale
IPC	Index of Phonetic Complexity
IRB	Institutional Review Board
ITT	Intention-To-Treat
KP	Knowledge of Performance
KR	Knowledge of Results
MOP	Manual of Procedures
NCT	National Clinical Trial
NIH	National Institutes of Health
OHRP	Office for Human Research Protections
OME	Oral mechanism examination
PI	Principal Investigator
PPVT	Peabody Picture Vocabulary Test
QA	Quality Assurance
QC	Quality Control
RCT	Randomized Controlled Trial
RIAS	Reynolds Intellectual Assessment Scales
SAE	Serious Adverse Event
SAS	Statistical Analysis Software
SCED	Single-Case Experimental Design
SD	Standard Deviation
SLAB Lab	Speech, Language, and Brain Laboratory
SLP	Speech-Language Pathologist
SOA	Schedule of Activities
SOP	Standard Operating Procedure
SRT	Syllable Repetition Task
T1,T2,T3	Timepoints 1, 2, and 3
TE	Teaching Episode
TOCS+	Test of Children's Speech Intelligibility
TU	Temple University
TUSLHC	Temple University Speech-Language-Hearing Center
UP	Unanticipated Problem
US	United States
WHO	World Health Organization

[illegible]

## Statistical Design and Power

### Power

As a Phase I trial of a novel treatment, this study is not powered to detect a definitive effect. Instead, realistic sample sizes for a summer camp at a single site will be used to estimate effect sizes for subsequent Phase 2 and Phase 3 trials and determine the potential need for a multisite trial. Nevertheless, for Aim 1, with sample sizes of 20 children per study,  $\alpha = 0.05$  (two-tailed), we expect to have at least 80% power to detect an ASSIST treatment effect size (mean difference between groups over the study period, divided by the pooled standard deviation) of 0.909 using a two-sample t-test. The only prior randomized controlled trial for CAS, with 26 children enrolled, reported effect sizes of 1.312 and 2.162 with only 12 hours of treatment (two different treatments), suggesting that the present study will have sufficient power to detect effects. For Aim 2, with sample sizes of 10 children per study,  $\alpha = 0.05$  (two-tailed), we expect to have at least 80% power to detect condition/intensity treatment effect size of 1.325 using a two-sample t-test. No power estimates were computed for secondary outcome measures.

### Statistical Design and Analysis Plan

Descriptive statistics (e.g., mean, median, standard deviation, skewness, and frequencies) will be computed for all variables to ensure data quality and evaluate assumptions of statistical tests. We will compare the pre-treatment performance between the immediate treatment groups and the control groups of each study to assess the success of randomization in producing two comparable groups. Although we do not expect any imbalance between the immediate treatment and control groups, we will adjust for any differences in our subsequent analyses to be sure any treatment effect is not due to potential confounds. For all analyses described in this study, we will use Statistical Analysis Software (SAS, v9.4, Cary, N.C.), with two-sided tests under presumed significant level of 0.05.

To address Specific Aim 1, independent two-sample t-tests will be used to compare gain scores (T1 to T2) from each proximal outcome measure, i.e., *speech accuracy of treated items* and *speech accuracy of generalization items*, between immediate treatment groups and the control groups with combined Studies 1 and 2 (**Figure 3**). A separate linear model will be fitted by adjusting for potential effect of study (Study 1/Study 2) to re-assess the initial efficacy of ASSIST.

To address Specific Aims 2a and 2b, independent two-sample t-tests will be used to compare gain scores from each proximal outcome measure, i.e., *speech accuracy of treated items* and *speech accuracy of generalization items*, between conditions (i.e., simple/complex, word/nonword). Gain scores will be based on T1 to T2 for Immediate groups and T2 to T3 for Delayed groups. Separate linear models will be fitted by adjusting for potential effect of ASSIST delivery time (Immediate/Delayed) to re-assess the parameters of *complexity* and *lexicality*.

To address Specific Aim 2c, independent two-sample t-tests will be used to compare gain scores (T1 to T3) from each proximal outcome measure, i.e., *speech accuracy of treated items* and *speech accuracy of generalization items*, between massed ASSIST group and the distributed ASSIST group. Because the Massed ASSIST group combines both Immediate Massed and Delayed Massed groups, no additional models will be fitted by adjusting potential effect of ASSIST delivery time (Immediate/Delayed) to re-assess the parameter of *intensity*.

To address Specific Aims 3a and 3b, the same analyses will be conducted as above for Studies 1-3, with the distal secondary outcome measures of parent ratings (communicative function, intelligibility) and objective intelligibility as dependent variables.

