9.4 STATISTICAL ANALYSES

9.4.1 GENERAL APPROACH

Descriptive statistics (e.g., mean, median, standard deviation, skewness, and frequencies) will be computed for all variables to ensure data quality and evaluate assumptions of statistical tests. We will

compare the pre-treatment performance between groups (ASSIST/No-ASSIST, Simple/Complex, Word/Nonword, Massed/Distributed) to assess the success of randomization in producing two comparable groups. Although we do not expect any imbalances between groups, we will adjust for any differences in our subsequent analyses to be sure any treatment effect is not due to potential confounds. For all analyses, we will use Statistical Analysis Software (SAS, v9.4, Cary, N.C.), with two-sided tests under presumed significant level of 0.05.

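### The SAP's baseline balance check, which triggers adjustment, names only the immediate/control pair; this fits Aim 1 but not Aims 2a-2c, and conflicts with Protocol 9.4.1 and 9.4.5

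*SAP*

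**What the plan says.** The SAP (Statistical Design and Analysis Plan) names one baseline contrast: "We will compare the pre-treatment performance between the immediate treatment groups and the control groups of each study to assess the success of randomization". The next sentence repeats that pair and makes it the trigger for adjustment: "Although we do not expect any imbalance between the immediate treatment and control groups, we will adjust for any differences in our subsequent analyses". The same section then tests three other contrasts: simple against complex, word against nonword, and, for Aim 2c, gain "between massed ASSIST group and the distributed ASSIST group".

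Protocol 9.4.1 has the same rule with different groups. It will "compare the pre-treatment performance between groups (ASSIST/No-ASSIST, Simple/Complex, Word/Nonword, Massed/Distributed) to assess the success of randomization in producing two comparable groups". Protocol 9.4.5 repeats it study by study: "We will compare the pre-treatment performance between groups in each study to assess the success of randomization in producing two comparable groups", and adds that "we will adjust for any differences in subsequent analyses to be sure any treatment effect is not due to potential confounds".

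The numbering differs. What the SAP calls combined Studies 1 and 2 are the protocol's Cycles 1 and 2. Below, Aim 1 is protocol Study 1, and Aims 2a, 2b and 2c are protocol Studies 2, 3 and 4.

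**The concern.** A balance check protects a comparison only if it looks at the arms being compared. The SAP promises that "we will adjust for any differences in our subsequent analyses to be sure any treatment effect is not due to potential confounds", but for three of its four comparisons it checks a different pair.

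Studies 2-4 have 10 children per arm and are analysed on change scores. If the compared arms differ by chance before treatment, regression to the mean shifts the expected difference in gain. An analyst following the SAP and one following the protocol could therefore fit different models to the same data, and neither document says which prevails. Protocol 4.1.3.4 adds a downstream stake, because the results of Studies 2 and 3 set the complexity and lexicality used in Study 4.

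**Working it through.** **1. The plan's own figures.** Two-sample t-test power comes from the noncentral t distribution with df = 2n - 2 and noncentrality d x sqrt(n/2).
- Studies 2-4: n = 10 per arm, d = 1.325, noncentrality 1.325 x 2.236 = 2.963, df = 18. Power is 80.0%, as stated.
- Study 1: n = 20 per arm, d = 0.909, noncentrality 0.909 x 3.162 = 2.875, df = 38. Power is 80.0%, as stated.

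Neither figure depends on the balance check.

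**2. Contrast checked against contrast tested.**

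| Aim | Tested | Checked under SAP | Checked under Protocol 9.4.1 |
|---|---|---|---|
| 1 | Immediate vs Delayed | Immediate vs control | ASSIST/No-ASSIST |
| 2a | Simple vs Complex | Immediate vs control | Simple/Complex |
| 2b | Word vs Nonword | Immediate vs control | Word/Nonword |
| 2c | Massed vs Distributed | Not defined | Massed/Distributed |

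**3. Aims 2a and 2b: the check is orthogonal.** Protocol 4.1.1 allocates 5:5:5:5 to Immediate-Simple, Immediate-Complex, Delayed-Simple and Delayed-Complex, with the same layout for Word/Nonword. In both baseline contrasts each child has weight +1/10 or -1/10. The covariance of the two contrasts is (5 - 5 - 5 + 5)/100 x variance = 0. The first is therefore uninformative about the second.

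**4. Aim 2c: the check is undefined.** Protocol 4.1.1 allocates 5 Massed Immediate, 5 Massed Delayed and 10 Distributed. The immediate/delayed split exists only inside the Massed arm.

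**5. Nothing else in the SAP fills the gap.** The extra models for Aims 2a and 2b adjust for delivery time, not for baseline performance. Aim 2c has no extra model.

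**6. Illustration of size.** Assumptions that are not in the documents: normal scores, equal pre and post SD, pre-post correlation r of 0.5 or 0.7, and 0.5 SD as a gap worth noticing.
- The SE of a 10 vs 10 baseline difference is sqrt(2/10) = 0.447 SD. P(gap at least 0.5 SD) = 2 x (1 - Phi(0.5/0.447)) = 26.4%. The chance is 9.4% for 0.75 SD and 2.5% for 1 SD.
- A baseline gap g shifts the expected gain difference by -(1 - r) x g, and the gain SD is sqrt(2(1 - r)). For g = 0.5 the shift is 0.25/1.000 = 0.25 gain SDs at r = 0.5, and 0.15/0.775 = 0.19 at r = 0.7. The effect size in the power calculation is 1.325.
- In simulation (400,000 layouts of 20 children for each r), among trials with a gap of at least 0.5 SD, type I error is about 9.6% (r = 0.5) or 7.6% (r = 0.7). Power at d = 1.325 is about 53-61% if the better arm starts higher and 93-96% if it starts lower.
- Over all trials, type I error is 5% and power 80%. In trials without such a gap, type I error is about 3.4-4.0%.

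**7. Dependence on the trigger.**
- If a gap of 0.5 SD is the trigger, the tested arms differ while the SAP check stays silent in 0.264 x 0.736 = 19.4% of trials.
- If the trigger is a two-sided test at 0.05, the right check flags only about 19% of such gaps, and the SAP's check about 4%. Trials in which the right check catches such a gap and the SAP's check misses it are then about 4.9%.

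**The case against.** The strongest reply is that the protocol already contains the correct rule. Sections 9.4.1 and 9.4.5 check each tested pair and adjust for differences. A reader of the SAP alone might infer that a Simple/Complex, Word/Nonword or Massed/Distributed imbalance goes unadjusted in this trial. The two documents together do not support that. It follows only if the SAP is applied without the protocol. This part of the reply stands.

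A reader might also infer that Studies 2-4 have inflated type I error or reduced power. They do not: the figures away from 5% and 80% appear only after selecting the unlucky quarter of randomisations. They describe any unadjusted change-score analysis under chance imbalance, and they do not isolate the effect of the SAP's wording. This also stands.

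Nor is harm shown when the SAP's check fires although the tested arms are balanced. If the adjustment that follows uses the baseline score, it would do no evident damage.

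Finally, naming the right pairs achieves little while neither document says what counts as a difference, which covariates enter, or in what model. That limits the benefit but does not make the SAP's pair correct. Reading the pair as loose shorthand is hard to sustain, since the SAP states it twice and uses the same terms for the Aim 1 groups only.

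**Conclusion.** The point holds as a conflict between documents and as a rule that is wrong as written in the SAP. The immediate/control check suits Aim 1, is orthogonal to the tested contrast in Aims 2a and 2b, and is undefined in Aim 2c. Steps 3 and 4 rest only on the stated allocation with full cells; dropout would make the orthogonality approximate.

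No stated sample size, power or alpha changes. The effect is conditional bias when the compared arms differ by chance at baseline: roughly 0.19 to 0.25 gain SDs for a 0.5 SD gap, under the assumed correlations. The share of trials in which the right check would catch such a gap and the SAP's would miss it runs from about 5% (significance-test trigger) to about 19% (0.5 SD trigger). Both triggers are assumptions. The correction should be made because it removes a conflict at almost no cost.

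**What to change.** In both SAP sentences, replace the immediate/control pair with the pair tested in each aim, matching Protocol 9.4.1. Tie any adjustment in an aim to that aim's own pair, on the pre-treatment score from which its gain is computed:
- Aim 1: Immediate vs Delayed, at T1.
- Aim 2a: Simple vs Complex, at T1 for Immediate children and T2 for Delayed children.
- Aim 2b: Word vs Nonword, at the same time points as Aim 2a.
- Aim 2c: Massed vs Distributed, at T1.

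For Aim 2b, add that both arms are compared on the same item set. One arm is treated on words and the other on nonwords, so a check on treated items would mix item difficulty with imbalance. Protocol 6.1.1.2.3 gives every child 30 words and 30 nonwords, so a common set exists; the SAP should say which is used.

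It would help to state in the same edit what counts as a difference and which covariate and model follow. Prespecifying baseline accuracy as a covariate in every study would remove the need for a trigger.

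Cost: two SAP sentences reworded and one added for Aim 2b. No new data, no extra children, and no change to the stated sample sizes or power.
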